**Safety Analysis****Primary Safety Endpoint:**

- The incidence of solicited adverse reactions within 7 days after vaccination.
- The CD4 / CD8 ratio delta compared to baseline.
- The incidence of unsolicited adverse events within 28 days after each vaccination.
- The incidence of detectable HIV viral load 24 and 52 weeks after vaccination
- The incidence of serious adverse events (SAE) and medically attended adverse events (MAE) within 52 weeks after vaccination in all participants.

Data from all participants will be used to assess the primary safety endpoint.

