Exclusion criteria	
Exclusion Criteria
 

• Participation in any other COVID-19 prophylactic drug trials for the duration of the study.

○ Note: Participation in COVID-19 treatment trials is allowed in the event of hospitalization due to COVID-19. The study team should be informed as soon as possible.

• Planned receipt of any vaccine (licensed or investigational), other than the study intervention, within 14 days before and after study vaccination.

• Prior receipt of an investigational or licensed vaccine likely to impact on the interpretation of the trial data (e.g. Adenovirus vectored vaccines, any coronavirus or SARS vaccines)

• Administration of immunoglobulins and/or any blood products within the three months prior to the planned administration of the vaccine candidate.

• Any confirmed or suspected immunosuppressive or immunodeficient state; asplenia; recurrent severe infections and chronic use (more than 14 days) of immunosuppressant medication within the past 6 months. Topical steroids or short-term (course lasting ≤14 days) oral steroids are not an exclusion.

• Active opportunistic infections or other AIDS-defining illness in the last six months.

• History of allergic disease or reactions likely to be exacerbated by any component of Ad5-nCoV

• Any history of angioedema

• Any history of anaphylaxis to any vaccine component

• Pregnancy, lactation or willingness/intention to become pregnant within 90 days after receiving study vaccine

• Current diagnosis of or treatment for cancer (except basal cell carcinoma of the skin and cervical carcinoma in situ)

• History of serious psychiatric condition likely to affect participation in the study

• Bleeding disorder (e.g. factor deficiency, coagulopathy or platelet disorder), or prior history of significant bleeding or bruising following IM injections or venepuncture

• Suspected or known current alcohol or drug dependency

• Severe and/or uncontrolled cardiovascular disease, respiratory disease, gastrointestinal disease, liver disease, renal disease, endocrine disorder and neurological illness (mild/moderate well-controlled comorbidities are allowed)

• History of laboratory-confirmed COVID-19

• Continuous use of anticoagulants, such as coumarins and related anticoagulants (i.e. warfarin) or novel oral anticoagulants (i.e. apixaban, rivaroxaban, dabigatran and edoxaban)

• Any other significant disease, disorder or finding which, in the opinion of the investigator, may significantly increase the risk to the volunteer because of participation in the study, affect the ability of the volunteer to participate in the study or impair interpretation of the study data.

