### **1.3. Rationale for the study**

Largely attributable to globalization, without a prophylactic vaccine against SARS-CoV-2, COVID-19 will persist as a pandemic threat [2]. The few published clinical trials support the need for further researching of the efficacy of receiving vaccines that will protect against SARS-CoV-2 infections [3].

This study is a phase IIb clinical trial to collect sufficient safety data to support the use of this candidate vaccine in HIV infected individuals.

Two doses of Ad5-nCoV at  $5 \times 10^{10}$ vp will be administered to adults of 18 years of age and older, living with HIV, on stable treatment.

The Adenovirus type 5 platform has been successfully used by CanSino Biologics in its licensed Ebola virus vaccine. Two phase I clinical trials in China and one phase II clinical trial in Sierra Leone of Recombinant Ebola Virus Disease Vaccine (Adenovirus Type 5 Vector, rAd5) were conducted. The safety data are summarized below.

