In its original version, the protocol limited inclusion to "people living with HIV on stable treatment and virologically suppressed..." .

Likewise, the design was double-blind versus placebo in a 2:1 ratio.

The advancement of the national vaccination reduced the possibilities of access to the study under such design, for which this protocol amendment was proposed.

Volunteers initially included in the study will receive two doses of the vaccine and will continue their follow-up as established in the protocol.

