#### **4.1 Inclusion Criteria**

1. Adults of 18 years of age, and older, with confirmed HIV infection according to criterion 2.
2. A positive rapid test or ELISA and/or a plasma HIV-1 viral load >1000 copies/ml or rapid test or ELISA plus a positive Western Blot test. In patients on antiretroviral treatment, a medical history summary or prescription signed and stamped by the treating physician is acceptable. Able and willing (in the Investigator's opinion) to comply with all study requirements.
3. Willing to allow the investigators to discuss the volunteer's medical history with their General Practitioner/personal doctor and access all medical records when relevant to study procedures.
4. Healthy adults, or stable-healthy adults who may have a pre-existing medical condition that does not meet any exclusion criteria. A stable medical condition is defined as disease not requiring significant change in therapy or hospitalization for worsening disease during the 3 months before enrolment [4].
5. For subjects of childbearing potential only: Willingness to practice continuous effective contraception (see glossary) for 30 days prior to enrolment in the study, for 90 days after receiving vaccination during the study, and have a negative pregnancy test on the day(s) of screening/ vaccination (First Injection Visit and Second Injection Visit).
6. Males participating in this study who are involved in heterosexual sexual activity must agree to practice adequate contraception (see glossary) and refrain from donating sperm for 90 days after receiving the study vaccination.
7. Agreement to refrain from blood donation during the study.
8. Provide written informed consent.

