#### **4.2 Exclusion Criteria**

1. Participation in any other COVID-19 prophylactic drug trials for the duration of the study.  
*Note: Participation in COVID-19 treatment trials is allowed in the event of hospitalization due to COVID-19. The study team should be informed as soon as possible.*
2. Planned receipt of any vaccine (licensed or investigational), other than the study intervention, within 14 days before and after study vaccination.

3. Prior receipt of an investigational or licensed vaccine likely to impact on the interpretation of the trial data (e.g. Adenovirus vectored vaccines, any coronavirus or SARS vaccines).
4. Administration of immunoglobulins and/or any blood products within the three months prior to the planned administration of the vaccine candidate.
5. Any confirmed or suspected immunosuppressive or immunodeficient state (other than living with HIV, on stable treatment, and virologically suppressed for at least 6 months); asplenia; recurrent severe infections and chronic use (more than 14 days) of immunosuppressant medication within the past 6 months. Topical steroids or short-term (course lasting  $\leq$ 14 days) oral steroids are not an exclusion.
6. Active opportunistic infections or other AIDS-defining illness in the last six months.
7. History of allergic disease or reactions likely to be exacerbated by any component of Ad5-nCoV.
8. Any history of angioedema.
9. Any history of anaphylaxis to any vaccine component.
10. Pregnancy, lactation or willingness/intention to become pregnant within 90 days after receiving study vaccine.
11. Current diagnosis of or treatment for cancer (except basal cell carcinoma of the skin and cervical carcinoma in situ).
12. History of serious psychiatric condition likely to affect participation in the study.
13. Bleeding disorder (e.g. factor deficiency, coagulopathy or platelet disorder), or prior history of significant bleeding or bruising following IM injections or venepuncture.
14. Suspected or known current alcohol or drug dependency.
15. Severe and/or uncontrolled cardiovascular disease, respiratory disease, gastrointestinal disease, liver disease, renal disease, endocrine disorder and neurological illness (mild/moderate well-controlled comorbidities are allowed).
16. History of laboratory-confirmed COVID-19.
17. Continuous use of anticoagulants, such as coumarins and related anticoagulants (i.e. warfarin) or novel oral anticoagulants (i.e. apixaban, rivaroxaban, dabigatran and edoxaban).

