### **5.1 Study Intervention Descriptions**

**All participants will be subject to the following procedures:**

- Informed consent**

The signed informed consent must be obtained before study participation. At each subsequent participant contact requiring an intervention (such as collection of a blood sample), the participant's consent will be verified.

- Check inclusion and exclusion criteria**

All inclusion and exclusion criteria will be checked at the screening in-person visit and will be reviewed at the second injection visit.

- Collect demographic data and participant contact information**

Record demographic data such as date of birth, sex, gender, height, weight and race in the participant's eCRF. Current email addresses and or phone numbers will be collected for each participant. It is important to have complete and accurate contact information for each participant as the majority of participant contacts will occur electronically. Contact information may also be used to remind participants of up-coming in-person visits.

- **Medical history**

Obtain the participant's medical history by interview and/or review of the participant's medical records and record any pre-existing conditions or signs and/or symptoms present in a participant prior to the first study injection in the eCRF. This will include reviewing any health condition that may prevent the participant from enrolling in the study, such as an unstable health condition. HIV treatment, clinical status, viral loads and CD4 counts will be reviewed.

- **HIV status, viral load, CD4 and CD8 counts**

At Screening visit, HIV status will be verified based on a previous serologic result or previous detectable viral load. Viral load samples, and CD4 and CD8 counts will be collected at Screening visit, and week 24 and week 52 visits. Screening visit value will be used as reference value for comparison with further values.

- **Baseline serology**

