### **9.3.3 Safety Analysis**

#### **Primary Safety Endpoint:**

- The incidence of solicited adverse reactions within 7 days after vaccination.
- The incidence of unsolicited adverse events within 28 days after vaccination.
- The incidence of detectable viral load 24 and 52 weeks after vaccination
- The incidence of serious adverse events (SAE) and medically attended adverse events (MAE) within 52 weeks after vaccination in all participants.

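### The primary HIV safety endpoint counts detectable viral load in all participants without regard to baseline, while the eligibility text conflicts on whether viraemic people may enter

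*Protocol*

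**What the plan says.** **Endpoint.** Section 9.3.3 lists among the primary safety endpoints "The incidence of detectable viral load 24 and 52 weeks after vaccination". The synopsis has the same item and closes its list of primary safety endpoints with "Data from all participants will be used to assess the primary safety endpoint". The intent-to-treat and per-protocol cohorts in Section 9.2 do not depend on entry viral load.

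**Baseline value.** Section 5.1 (HIV status, viral load, CD4 and CD8 counts) says "Screening visit value will be used as reference value for comparison with further values", and the synopsis repeats this. For participants first assigned to placebo, Table 2 marks the viral load sample at Week 24 and Week 52 only, not at Visit 1.B, when they receive their first active dose.

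**Who may enter.**
- Section 1.3, on the amendment: "In its original version, the protocol limited inclusion to" people on stable treatment who were virologically suppressed.
- Section 1.3, on the present study: vaccine "will be administered to adults of 18 years of age and older, living with HIV, on stable treatment".
- Section 4.1, criterion 1: "Adults of 18 years of age, and older, with confirmed HIV infection according to criterion 2". Neither Section 4.1 nor the synopsis inclusion list requires suppression.
- Section 4.2, criterion 5, excludes immunodeficient states "other than living with HIV, on stable treatment, and virologically suppressed for at least 6 months".
- The synopsis version of that exclusion reads "Any confirmed or suspected immunosuppressive or immunodeficient state; asplenia; recurrent severe infections" and contains no exemption for HIV.

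**Aim.** Section 9.1 describes an uncontrolled, open study intended to show what vaccination does to the course of HIV.

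**The concern.** The endpoint is a status measured after vaccination. It does not record a change. A participant who was detectable at screening and is still detectable at Week 24 counts the same as one who was suppressed and lost control after vaccination. Only the second is informative about harm. The other HIV markers in Section 9.3.3 are handled differently: CD4+ is a fall of at least 20%, and CD4/CD8 is a difference from the basal value. The primary marker is the one not tied to baseline.

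Without a control arm, each participant's own baseline is the only comparator. If it is not used, entry viraemia can look like a vaccine effect. Falling viraemia among those detectable at entry can equally hide new viraemia among the suppressed. Because the eligibility passages conflict, the four sites could read them differently and enroll different populations, so the same percentage could mean different things by site.

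**Working it through.** **1. Inputs.** The planned N is 500 (Section 3.2). Section 9.1 says the sample size has no statistical basis, and the protocol gives no viral load rate. There is therefore no figure in the plan to reproduce, and b, r and v below are all assumptions:
- b: share of participants detectable at entry
- r: share of those still detectable at the visit
- v: share of the others who become newly detectable

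**2. Eligibility passages side by side.** The amendment text in Section 1.3 places the suppression limit in the original version. The current inclusion lists do not contain it, and their special proof of HIV for patients on antiretroviral treatment implies that some entrants may not be on treatment. Exclusion 5 in Section 4.2 still exempts HIV only when treated and suppressed for at least 6 months. The synopsis exclusion has no HIV exemption at all. Section 1.3 also describes the population as on stable treatment. These current statements do not describe one population. The inclusion route through a viral load above 1000 copies/ml is a way to confirm HIV and does not by itself show viraemia at entry, so nothing here rests on it.

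**3. Size if viraemic people enter.** Observed proportion = b·r + (1 − b)·v, with v = 3%:

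| b | r | b·r | (1 − b)·v | Observed | Share pre-existing |
|---|---|---|---|---|---|
| 0% | – | 0 | 3.00% | 3.0% | 0% |
| 5% | 30% | 1.50% | 2.85% | 4.35% | 34% |
| 10% | 50% | 5.00% | 2.70% | 7.7% | 65% |
| 10% | 80% | 8.00% | 2.70% | 10.7% | 75% |
| 20% | 50% | 10.00% | 2.40% | 12.4% | 81% |
| 20% | 80% | 16.00% | 2.40% | 18.4% | 87% |

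In the third row, 7.7% of 500 is 38.5 expected events, of which 0.10 × 0.50 × 500 = 25 were there before vaccination.

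**4. Range.** With b from 2% to 20%, v from 1% to 5% and r from 30% to 100%, in whole participants, the all-participant rate runs from 1.6% to 24.0% and the pre-existing share from 11% to 96%. The rate among those undetectable at screening stays at about 1% to 5%. For example, with b = 10%, r = 60% and v = 3%, the all-participant rate is 44/500 = 8.8% (exact 95% CI 6.5% to 11.6%). The restricted rate is 14/450 = 3.1% (1.7% to 5.2%).

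**5. Masking.** With b = 20%:
- r = 50%, v = 3%: 0.20 × 0.50 + 0.80 × 0.03 = 12.4%
- r = 38%, v = 6%: 0.20 × 0.38 + 0.80 × 0.06 = 12.4%

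New viraemia has doubled and the endpoint has not moved.

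**The case against.** The strongest reply is that inclusion and exclusion criteria apply together. A silent inclusion list combined with exclusion 5 keeps viraemic people out, and the reference to stable treatment in Section 1.3 points the same way. On that reading b = 0 and the bias disappears. That consequence is accepted. The reading does not settle the text, however: the protocol itself assigns the suppression limit to its original version, the current inclusion lists lack it, and the same exclusion is worded differently in the synopsis and the body.

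Second, incidence can mean new occurrence, the screening value is named as the reference, and detail may be left to the SAP. The data needed are indeed collected. But the protocol itself fixes the endpoint, and its synopsis fixes the population, without linking either to that reference. The eligibility conflict is not a matter for the SAP. It is fair to say that the all-participants sentence is a general one covering several endpoints and appears only in the synopsis; even so, the body sets no baseline condition either.

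Third, the rates are hypothetical. Those enrolled under the original version were limited to suppressed people, so entry viraemia would come mainly from later enrollees and a b of 20% overall is harder to reach. The masking example needs two changes that happen to offset. Both points stand and limit the likely size. The same history means that the missing Visit 1.B sample gives former placebo recipients an old reference value; it is not evidence of entry viraemia.

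Fourth, a shift table or screening and follow-up proportions shown together would use the same data. A shift table would separate new from persisting viraemia. Two marginal proportions would not.

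**Conclusion.** The concern holds. As written, the primary HIV endpoint cannot separate new from persisting viraemia, and the protocol does not state consistently whether viraemic people may enter. The size depends wholly on how many do: none if exclusion 5 is applied literally, 4.35% instead of 3.0% at b = 5% and r = 30%, and 7.7% at b = 10% and r = 50%. These are illustrations under assumed rates. They show that a small viraemic minority would be enough to dominate the count; they do not show that bias has occurred. This should be fixed before the viral load analysis. Confidence is medium, because the effect rests on an eligibility rule that the protocol leaves open.

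**What to change.** 1. Define the primary analysis as new detectable viral load at Week 24 and Week 52 among participants undetectable at the screening reference value, with an exact 95% confidence interval.
2. For participants detectable at screening, report the paired change in log10 viral load separately.
3. Show former placebo recipients separately or flag them, because their reference value predates the placebo period.
4. Reconcile the synopsis criteria, both statements in Section 1.3, and Sections 4.1 and 4.2 into one eligibility statement. Which rule is right is for the sponsor to settle.

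**Cost.** Low. The screening viral load is already collected, so items 1 to 3 need no new sample. The denominator shrinks if viraemic people enter. At a 3% event rate the exact interval is 1.7% to 4.9% with 15/500, and 1.6% to 5.2% with 12/400 (20% viraemic at entry). The change cannot give former placebo recipients a value taken just before their first active dose.

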#### **Secondary Safety Objective Endpoints**

- The incidence of a decrease in CD4+ cell count by  $\geq 20\%$  at 24 and 52 weeks after vaccination
- The delta in the CD4/CD8 rate compared to the basal value.

All SAEs will be listed and summarized by groups.

For each participant, the individual local events will be aggregated into a combined event "Local", which is the maximum severity of the individual local events. For each participant, the individual general events will be aggregated into a combined event "General", which is the maximum severity of the individual general events. An aggregate event "Any" will be defined as the maximal severity of the combined events "Local" and "General". In addition to being graded for severity as mild, moderate or severe, the severity of all events will be graded as "Any", which will include mild, moderate or severe events, and "Significant" which will include moderate or severe events.

All statistical tests on safety performed will be 2-sided with Type I error of 5%. Missing values will not be included in the safety analyses, and there will be no imputation of missing values. No adjustments will be made for multiple comparisons.

For the analysis of proportions, binomial point estimates and exact binomial confidence intervals will be calculated.

Fisher's Exact Test will be used to assess differences in rates of adverse events between treatment and control groups.

In addition, all safety data will be analysed descriptively, including unsolicited events collected through the end of the observation period.

The Safety analysis will be performed based on the intent-to-treat cohort and per-protocol cohort.

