#### 3.2 Study Groups

A total of 500 participants will be enrolled to receive the vaccine. All participants will be monitored for solicited adverse events for 7 days, unsolicited adverse events for 28 days, SAEs and MAEs for the one year duration of the study, and antibody measurements at baseline, Day 28, Day 84, week 24, and week 52. A subset of 50 participants will have cellular immunity measured at those same intervals.

This protocol amendment provides for unblinding of participants who were entered into the study in the double-blind schedule. For participants who entered the double-blind schedule, the visit process will be as follows:

a) Sites will receive an unblinding list detailing participants who received placebo or study vaccine. Participants who received placebo will be invited to continue in the study under the

open-label study scheme and should make visits from V1.B (first vaccine) onwards, after signing the informed consent, completing visits on day 28 (V2.B), day 56 (second dose) (V3.B), day 84 (V4.B), week 24 (V5.B) and week 52 (V6.B). In this group of participants already enrolled, no antibody dosage collection will be performed at the V1B visit; the V1 values at study entry will be taken. The letter B is added to the visits to differentiate this group of participants who must reorganize the schedule of visits from the administration of the first dose of CoVID vaccine after the unblinding. The procedures for this group are detailed in Table 2.

b) Participants who, after the unblinding, are found to have received study vaccine at the initial visit, will complete the visits established by protocol together with the administration of dose 2 of the study (day 56) onwards, after signing the informed consent. In this group of participants there will be no changes in the nomenclature of the visits.

For both arms (placebo and study vaccine), efficacy contacts are restarted with the second injection visit.

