## 9. OUTCOME MEASURES AND STATISTICAL METHODS

### 9.1 Sample Size Estimation

Since this is an open, non-comparative study that seeks to observe the impact of vaccination on the evolution of HIV disease, a sample size defined by statistical criteria is not established.

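### The primary HIV viral-load endpoint is fixed as an available-case analysis with imputation barred, so detectable viral load may be understated if those who miss the draw are more often viraemic

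*Protocol*

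**What the plan says.** Section 9.3.3 of the protocol lists among the primary safety endpoints "The incidence of detectable viral load 24 and 52 weeks after vaccination". The synopsis has the same endpoint, and Section 9.1 describes an open, uncontrolled study that "seeks to observe the impact of vaccination on the evolution of HIV disease".

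On sampling, Section 5.1 states: "Viral load samples, and CD4 and CD8 counts will be collected at Screening visit, and week 24 and week 52 visits". Tables 1 and 2 show no other viral-load draw after the first vaccination.

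On estimation, Section 9.3.3 states: "For the analysis of proportions, binomial point estimates and exact binomial confidence intervals will be calculated". On missing data, the same section and the synopsis state: "Missing values will not be included in the safety analyses, and there will be no imputation of missing values". Neither place makes an exception for viral load or names a sensitivity analysis for missing values.

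The safety analysis is run in two cohorts. Under Section 9.2.1 the intent-to-treat cohort keeps a withdrawn participant only up to the withdrawal date. The per-protocol cohort is a narrower subset of it. Section 8.2 does not replace anyone who withdraws after the first dose.

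On size, Section 3.2 states: "A total of 500 participants will be enrolled to receive the vaccine". Section 9.1 adds that "a sample size defined by statistical criteria is not established". No expected dropout rate or expected proportion with detectable viral load is given.

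**The concern.** A missed Week 24 or Week 52 draw is a missing primary outcome with no back-up. Serious and medically attended events are different, because four-weekly calls also collect them.

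The proportion among attenders equals the proportion in the whole cohort only if attenders and non-attenders have the same detectable rate. Disengagement from HIV care could plausibly cause both a missed visit and a detectable viral load. Section 1.3 says the protocol first limited entry to people who were virologically suppressed. The inclusion criteria in Section 4.1 no longer do so, although exclusion criterion 5 in Section 4.2 still mentions suppression. Viral control in the cohort may therefore vary more than it once would have.

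No concurrent control arm shares the attrition, so any distortion passes directly into the single reported proportion. The exact interval describes binomial sampling error among those observed and nothing else. A reader could take a low proportion with a tight interval as more secure than it is.

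**Working it through.** The protocol states no figure to reproduce for this endpoint, so the check is conditional.

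**Inputs from the protocol.** N = 500 vaccinated participants (Section 3.2). Exact binomial interval (Section 9.3.3). I take 95% confidence to match the two-sided 5% level given there for safety tests.

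**Inputs assumed.** 5%, 10% or 20% of draws missing at a given visit. About 5% detectable among attenders, with 10% as a second case. The detectable rate among the missing, q, runs from 0 to 1.

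**Formulas.** With n attenders, x of them detectable, and m = 500 − n missing:

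- Planned estimate: x/n. Clopper-Pearson limits are the 0.025 quantile of Beta(x, n − x + 1) and the 0.975 quantile of Beta(x + 1, n − x).
- Full-cohort rate: (x + q·m)/500.
- Tipping point, where the full-cohort rate reaches the planned upper limit U: q = (500·U − x)/m.

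**Worked case, 10% missing.** x/n = 22/450 = 4.9%, 95% CI 3.1-7.3%.

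- q = 0: 22/500 = 4.4%
- q = 10%: (22 + 5)/500 = 5.4%
- q = 25%: (22 + 12.5)/500 = 6.9%
- q = 50%: (22 + 25)/500 = 9.4%
- q = 1: (22 + 50)/500 = 14.4%
- Tipping point: (500 × 0.073 − 22)/50 = 14.5/50, about 29%

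**All three missing rates, about 5% detectable among attenders.**

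| Missing | x/n | Planned result (95% CI) | q = 0 | q = 10% | q = 25% | q = 50% | q = 1 | Tipping q |
|---|---|---|---|---|---|---|---|---|
| 5% (25) | 24/475 | 5.1% (3.3-7.4) | 4.8% | 5.3% | 6.0% | 7.3% | 9.8% | about 52% |
| 10% (50) | 22/450 | 4.9% (3.1-7.3) | 4.4% | 5.4% | 6.9% | 9.4% | 14.4% | about 29% |
| 20% (100) | 20/400 | 5.0% (3.1-7.6) | 4.0% | 6.0% | 9.0% | 14.0% | 24.0% | about 18% |

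**Second case, about 10% detectable among attenders.** The full-cohort range is 9.6-14.6% with 5% missing (tipping point about 71%), 9.0-19.0% with 10% missing (about 42%) and 8.0-28.0% with 20% missing (about 27%).

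**Direction.** The attender-only rate is too low only when q exceeds x/n. It is right when the two are equal, and too high when q is smaller.

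**Do the two cohorts cover this?** No. Both are subject to the same missing-value rule, and a participant included only up to withdrawal contributes no later viral load.

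**The case against.** A reader might infer that viral rebound will be understated. The documents do not support that, for two reasons. First, the direction is not shown: there is no dropout rate, no detectable rate, and nothing linking a missed visit to being out of care. Section 8.2 lists withdrawal reasons, such as moving away, that need have no connection with viral control. Second, rebound is not the endpoint. The endpoint counts any detectable value, and since inclusion no longer requires suppression, some participants may be detectable at entry.

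A reader might also infer that a claim of no harm is undermined. Section 9.1 describes an observational aim, and the protocol states no margin, hypothesis or criterion for this endpoint, so there is no such claim to fail.

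Moderate departures also do little. With 10% missing, q = 10% (about twice the attenders' rate) and q = 25% (about five times) both leave the full-cohort rate inside the planned interval. The protocol works to limit missed visits through weekly contacts, four-weekly calls, ±14-day windows, attempts to reach non-returners and visit stipends.

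Counting missing as detectable mixes retention with viraemia, and without a comparator it cannot separate the two. It bounds the proportion but does not measure vaccine harm.

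Finally, Section 9.3 leaves details of methods to the SAP, which is not at hand and may add bounds.

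Most of this stands and limits the point. The last argument answers only part of it: the protocol itself makes the choice, and an SAP that counted missing as detectable would contradict the wording of Section 9.3.3.

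**Conclusion.** The point holds in a conditional form. The protocol fixes an available-case analysis and bars imputation for a primary safety endpoint that is measured after entry at only two visits, in a study without a concurrent control. It provides no check on the assumption this needs. If non-attenders are more often viraemic than attenders, the proportion with detectable viral load may be understated, and the exact interval will not show it.

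The possible size depends mainly on how many draws are missed. At about 5% detectable among attenders, the full-cohort rate could be at most 9.8% with 5% missing, 14.4% with 10% and 24.0% with 20%, against planned upper limits of 7.4%, 7.3% and 7.6%. These are bounds under assumed rates, not predictions. The available-case estimate remains usable, and the change is worth making because it is cheap.

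**What to change.** Keep the available-case proportion with its exact interval as the main estimate. In Section 9.3.3 and the matching synopsis text, exempt detectable viral load from the bar on imputation. Then:

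- Report the number of missing viral loads at Week 24 and at Week 52, by baseline viral-load status and, for those who withdrew, by the reason already recorded under Section 8.2.
- Pre-specify a sensitivity analysis counting missing as detectable, with either the best-to-worst-case range or a tipping point.
- Interpret the observed proportion alongside these figures. No pass-or-fail rule should be attached, because the protocol has no threshold to apply it to.

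The sensitivity analysis should not depend on the last known antiretroviral status. Section 6.2 requires routine recording of concomitant medication only up to 28 days after a dose, which is about Day 84 (56 + 28), so status near Weeks 24 and 52 is not clearly captured.

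The cost is a few table rows, with no new visits, samples or participants. The sensitivity figure will look less favourable than the main estimate and will partly reflect retention; the report should say so.
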